3.1.1.5. Serious Adverse Events

SAEs will be collected from the time the participant or participant's parent(s)/legal guardian provides informed consent through approximately 6 months after the study vaccination. SAEs will be categorized according to MedDRA terms. The primary safety endpoint "SAEs from vaccination through 6 months after the study vaccination" will be summarized, by SOC and PT, at the participant level for each group. Additionally, SAEs will be listed.

3.1.2. Primary Immunogenicity Endpoints

In participants without evidence of SARS-CoV-2 infection and in participants with and without evidence of SARS-CoV-2 infection:

Cohort 1:

- SARS-CoV-2 Omicron (BA.2)—neutralizing titers at baseline and 1 month after the study vaccination
- SARS-CoV-2 Omicron (BA.1)—neutralizing titers at baseline and 1 month after the study vaccination
- SARS-CoV-2 reference-strain—neutralizing titers at baseline and 1 month after the study vaccination

Cohort 2:

- SARS-CoV-2 Omicron (BA.4/BA.5)—neutralizing titers at baseline and 1 month after the study vaccination
- SARS-CoV-2 Omicron (BA.1)—neutralizing titers at baseline and 1 month after the study vaccination
- SARS-CoV-2 reference-strain—neutralizing titers at baseline and 1 month after the study vaccination

Cohort 2/Group 2 + Cohort 3/Group 1 combined and Cohort 2/Group 4 + Cohort 3/Group 2 combined:

In participants with and without evidence of SARS-CoV-2 infection:

• SARS-CoV-2 Omicron (BA.4/BA.5)—neutralizing titers at 1 month after the study vaccination

Cohort 4:

- SARS-CoV-2 Omicron (BA.4/BA.5)—neutralizing titers at baseline and 1 month after the study vaccination
- SARS-CoV-2 reference-strain—neutralizing titers at baseline and 1 month after the study vaccination

3.2. Secondary Endpoint(s)

Cohort 2/Group 4 + Cohort 3/Group 2 combined (>55-year age group):

In participants with and without evidence of SARS-CoV-2 infection:

• SARS-CoV-2 reference-strain—neutralizing titers at 1 month after the study vaccination

Cohort 2/Group 2 + Cohort 3/Group 1 combined and Cohort 2/Group 4 + Cohort 3/Group 2 combined:

In participants without evidence of SARS-CoV-2 infection and in participants with and without evidence of SARS-CoV-2 infection:

- SARS-CoV-2 Omicron (BA.4/BA.5)—neutralizing titers at 1 month after the study vaccination
- SARS-CoV-2 reference-strain—neutralizing titers at 1 month after the study vaccination

3.3. Exploratory Endpoint(s)

Cohort 1:

- SARS-CoV-2 Omicron (BA.2)—neutralizing titers at baseline and 7 days, 1 month, 3 months, and 6 months after the study vaccination
- SARS-CoV-2 Omicron (BA.1)—neutralizing titers at baseline and 7 days, 1 month, 3 months, and 6 months after the study vaccination

• SARS-CoV-2 reference-strain—neutralizing titers at baseline and 7 days, 1 month, 3 months, and 6 months after the study vaccination

Cohort 2/Group 1, Cohort 2/Group 2 + Cohort 3/Group 1 combined, Cohort 2/Group 4 + Cohort 3/Group 2 combined, Cohort 2/Group 3, and Cohort 2/Group 5:

- SARS-CoV-2 Omicron (BA.4/BA.5)—neutralizing titers at baseline and 1 month, 3 months, and 6 months after the study vaccination
- SARS-CoV-2 reference-strain—neutralizing titers at baseline and 1 month, 3 months, and 6 months after the study vaccination

Cohort 4:

- SARS-CoV-2 Omicron (BA.4/BA.5)—neutralizing titers at baseline and 7 days, 1 month, 3 months, and 6 months after the study vaccination
- SARS-CoV-2 reference-strain—neutralizing titers at baseline and 7 days, 1 month, 3 months, and 6 months after the study vaccination

Cohort 1, Cohort 2 + Cohort 3 combined, and Cohort 4:

- Confirmed COVID-19 cases
- Confirmed severe COVID-19 cases
- Strain sequencing of COVID-19 cases
- SARS-CoV-2—neutralizing titers previously specified for the respective cohorts at the COVID-19 illness visit and the convalescent visit
- SARS-CoV-2—neutralizing titers for other emerging variants (under monitoring, of interest, and/or of concern) not already specified

Cohort 2:

 Cell-mediated immune response, and additional humoral immune response parameters, to the reference strain and Omicron in a subset of participants with PBMC samples collected in each group

3.4. Baseline Variables

Measurements or samples collected prior to the study vaccination are considered the baseline data for the assessments.

3.4.1. Demographics, Medical History, and Physical Examination

The demographic variables will be collected including date of birth, sex (male or female), race (Black or African American, American Indian or Alaskan native, Asian, Native Hawaiian or other Pacific Islander, White, multiracial, unknown, and not reported), ethnicity (Hispanic/Latino or of Spanish origin, non-Hispanic/non-Latino or not of Spanish origin, and not reported), and BMI. In cases where more than 1 category is selected for race, the participant would be counted under the category "multiracial" for analysis.

Age at the time of the study vaccination (in years) will be derived based on the participant's birthday. For example, if the study vaccination day is 1 day before the participant's 20th birthday, the participant is considered to be 19 years old.

Medical history will be collected and categorized according to the current version (at the time of reporting) of MedDRA.

If the clinical assessment indicates that a physical examination is necessary to comprehensively evaluate the participant, a physical examination will be performed. Physical examination findings collected during the study will be considered source data and will not be required to be reported, unless otherwise noted.

3.4.2. E-Diary Transmission

An e-diary will be considered transmitted if any data for the local reactions, systemic events, or use of antipyretic medication are present for any day. If all data are missing for all the items on the e-diary for all 7 days after vaccination, the e-diary will be considered not transmitted.

3.4.3. Prior/Concomitant Vaccines and Concomitant Medications

The following prior and concomitant medications and vaccinations will be recorded in the CRF:

- Prohibited medications listed in the protocol, Section 6.9.1, will be recorded in the concomitant medication CRF (with the exception of prophylactic antipyretics and other pain medication to prevent symptoms) to include start and stop dates, name of the medication, dose, unit, route, and frequency.
- All vaccinations received from 28 days prior to study enrollment until the 6-month follow-up visit will be recorded in the nonstudy vaccination CRF.
- All prior COVID-19 vaccinations will be recorded in the prior COVID-19 vaccination CRF.

- Any prescribed medication to treat or intended to treat COVID-19/MIS-C illness, including receipt of antiplatelets (eg, aspirin, clopidogrel) or anticoagulants (eg, heparin, enoxaparin, warfarin), will be recorded in the concomitant medication CRF within the COVID-19 illness visit.
- Prior and concomitant vaccines and concomitant medications will be coded using the WHO Drug Dictionary.

3.5. Safety Endpoints

Local reactions, systemic events, AEs, and SAEs have been described above in the Primary Safety Endpoints section (Section 3.1.1).

4. ANALYSIS SETS (POPULATIONS FOR ANALYSIS)

Analysis populations are defined for the statistical analysis of safety and immunogenicity results in the table below. Data for all participants will be assessed to determine if participants meet the criteria for inclusion in each analysis population prior to unblinding and releasing the database and classifications will be documented per standard operating procedures.

Population	Description
Screened	All participants who have a signed ICD.
Randomized/assigned	All participants who are assigned a randomization number in the IRT system.
Evaluable immunogenicity	All eligible randomized/assigned participants who receive the study intervention to which they are randomized/assigned, have at least 1 valid and determinate immunogenicity result from the blood sample collected within 28-42 days after the study vaccination, and have no other important protocol deviations as determined by the clinician.
All-available immunogenicity (mITT)	All randomized/assigned participants who receive the study intervention with a valid and determinate immunogenicity result after vaccination.
Safety	All participants who receive the study intervention.

Important protocol deviations will be determined by the medical monitor. An important protocol deviation is a protocol deviation that, in the opinion of the sponsor's clinician, would materially affect assessment of immunogenicity, eg, participant receipt of a prohibited vaccine or medication that might affect immune response or a medication error with suspected decrease in potency of the vaccine. The sponsor's medical monitor will identify those participants with important protocol deviations that result in exclusion from analysis populations.

The safety analyses are based on the safety population. Participants will be summarized by vaccine group according to the study interventions they received. In general, completely missing reactogenicity data (ie, all 7 days of collection are missing) will not be imputed. For partially missed reactogenicity data (eg, 1-6 days of reactogenicity data are available), it is assumed that no reactions or events were experienced on the missing days; missing AE dates will be handled according to the Pfizer safety rules.

For all the immunogenicity endpoints, the analysis will be based on the evaluable immunogenicity population. An additional analysis may be performed based on the all-available immunogenicity population if there is a ≥10% difference in sample size between the all-available immunogenicity population and the evaluable immunogenicity population. Participants will be summarized according to the vaccine group to which they were randomized/assigned. Missing serology data will not be imputed.

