9.3.1. General Considerations

CIs for all endpoints in the statistical analysis will be presented as 2-sided at the 95% level unless specified otherwise.

The safety analyses are based on the safety population. Participants will be summarized by vaccine group according to the study interventions they actually received.

For all the immunogenicity endpoints, the analysis will be based on the evaluable immunogenicity population. An additional analysis may be performed based on the all-available immunogenicity population if there is a large enough difference in sample size between the all-available immunogenicity population and the evaluable immunogenicity population. Participants will be summarized according to the vaccine group to which they were randomized.

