2.2. Study Objectives, Endpoints, and Estimands

The estimands corresponding to each primary, secondary, and exploratory objectives are described in Table 2 below.

In the primary safety objective evaluations, missing AE start dates will be imputed according to Pfizer safety rules (Section 5.3). In general, completely missing reactogenicity data (ie, all 7 days of collection are missing) will not be imputed. For the partially missed reactogenicity data (ie, 1-6 days of reactogenicity data are available), it is assumed that no reactions or events were experienced on the missing days.

The estimands to evaluate the immunogenicity objectives are based on evaluable populations for immunogenicity (see Section 4 for definition). These estimands estimate the vaccine effect in the hypothetical setting where participants follow the study schedules and protocol requirements as directed. Missing antibody results will not be imputed. Immunogenicity results that are below the LLOQ will be set to $0.5 \times LLOQ$ in the analysis; this may be adjusted once additional data on the assay characteristics become available.

Table 2. List of Objectives, Endpoints, and Estimands

Objectives	Estimands	Endpoints
	Primary Safety	
Cohort 1: To describe the safety and tolerability profile of BNT162b5 Bivalent (WT/OMI BA.2) 30 µg and BNT162b2 Bivalent (WT/OMI BA.1) 30 µg given as a second booster dose to COVID-19 vaccine–experienced participants 18 through 55 years of age	 In participants receiving 1 dose of study intervention, the percentage of participants reporting: Local reactions for up to 7 days following the study vaccination Systemic events for up to 7 days following the study vaccination AEs from the study vaccination through 1 month after the study vaccination SAEs from the study vaccination through 6 months after the study vaccination 	 Local reactions (pain at the injection site, redness, and swelling) Systemic events (fever, fatigue, headache, chills, vomiting, diarrhea, new or worsened muscle pain, and new or worsened joint pain) AEs SAEs

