6.1.2.2. Cohort 2 and Cohort 3 Combined

6.1.2.2.1. Main Analysis

In participants with and without evidence of SARS-CoV-2 infection:

For Superiority Hypothesis Test

- Estimands: GMRs of Omicron (BA.4/BA.5)—neutralizing titers at 1 month after BNT162b2 Bivalent (WT/OMI BA.4/BA.5) 30 μg for Cohort 2/Group 4 + Cohort 3/Group 2 combined to 1 month after BNT162b2 given as a second booster dose for C4591031 Substudy E Group 1.
- Analysis set: Evaluable immunogenicity population, all-available immunogenicity population (as applicable) (Section 4).
- Analysis time point: 1 Month after vaccination.
- Analysis methodology: Model-based GMRs and the associated 2-sided 95% CIs along with the model-based LS GMT and associated 2-sided 95% CIs will be calculated using the linear regression model that includes terms for baseline neutralizing titer and comparison group. Statistical method is described in Section 5.2.4.

- Intercurrent events and missing data: Serology data deemed unevaluable because of noncompliance with the key protocol criteria will be excluded. Missing data will not be imputed.
- Reporting results: The LS GMT and associated 95% CIs from each comparison group, as well as the model-based GMR with their associated 95% CIs, will be summarized.

For Noninferiority Hypothesis Test

- Estimands:
 - O The difference in percentages of participants with seroresponse to the Omicron strain (BA.4/BA.5) at 1 month after BNT162b2 Bivalent (WT/OMI BA.4/BA.5) 30 μg for Cohort 2/Group 4 + Cohort 3/Group 2 combined to 1 month after BNT162b2 given as a second booster dose for C4591031 Substudy E Group 1
 - GMRs of Omicron (BA.4/BA.5)—neutralizing titers at 1 month after BNT162b2 Bivalent (WT/OMI BA.4/BA.5) 30 μg for Cohort 2/Group 2 + Cohort 3/Group 1 combined to 1 month after BNT162b2 Bivalent (WT/OMI BA.4/BA.5) 30 μg for Cohort 2/Group 4 + Cohort 3/Group 2 combined
 - The difference in percentages of participants with seroresponse to the Omicron strain (BA.4/BA.5) at 1 month after BNT162b2 Bivalent (WT/OMI BA.4/BA.5) 30 µg for Cohort 2/Group 2 + Cohort 3/Group 1 combined to 1 month after BNT162b2 Bivalent (WT/OMI BA.4/BA.5) 30 µg for Cohort 2/Group 4 + Cohort 3/Group 2 combined
- Analysis set: Evaluable immunogenicity population, all-available immunogenicity population (as applicable) (Section 4).
- Analysis time point: 1 Month after vaccination.

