6.1.2.2.2. Sensitivity Analysis

To support the interpretation of the primary analysis, the unadjusted GMTs and 95% CIs will be provided for each comparison group, both before the study vaccination and 1 month after vaccination. The unadjusted GMR and 95% CIs will also be calculated based on the Student t distribution. Statistical methods are described in Section 5.2.4.

The unadjusted difference in percentages of participants with seroresponse between the 2 comparison groups and the associated 2-sided 95% CIs will be calculated using the Miettinen and Nurminen method. Statistical methods are described in Section 5.2.1.

Supportive analyses in participants without evidence of SARS-CoV-2 infection may also be performed.

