6.2. Secondary Endpoint(s)

6.2.1. Secondary Immunogenicity Endpoints

6.2.1.1. Main Analysis

For Noninferiority Hypothesis Test

For the >55-year age group (Cohort 2/Group 4 + Cohort 3/Group 2 combined): In participants with and without evidence of SARS-CoV-2 infection:

- Estimands: GMRs of reference-strain–neutralizing titers at 1 month after BNT162b2 Bivalent (WT/OMI BA.4/BA.5) 30 μg for Cohort 2/Group 4 + Cohort 3/Group 2 combined to 1 month after BNT162b2 given as a second booster dose for C4591031 Substudy E Group 1.
- Analysis set: Evaluable immunogenicity population, all-available immunogenicity population (as applicable) (Section 4).
- Analysis time point: 1 Month after vaccination.

- Analysis methodology: Model-based GMRs and the associated 2-sided 95% CIs along with the model-based LS GMTs and associated 2-sided 95% CIs for each group will be calculated using the linear regression model that includes terms for baseline neutralizing titer and comparison group. Statistical method described in Section 5.2.4.
- Intercurrent events and missing data: Serology data deemed unevaluable because of noncompliance with the key protocol criteria will be excluded. Missing data will not be imputed.
- Reporting results: The LS GMTs and associated 95% CIs from each comparison group, as well as the model-based GMR with the associated 95% CI, will be summarized.
- Supportive Analysis: As supportive analysis, the unadjusted GMTs and 95% CIs before study vaccination and 1 month after vaccination will be provided for each comparison group. The unadjusted GMR and 95% CIs will also be calculated based on the t distribution. Statistical methods are described in Section 5.2.4. The same analyses in participants without evidence of SARS-CoV-2 infection may also be performed as supportive.

For Descriptive Summary

For Cohort 2/Group 2 + Cohort 3/Group 1 combined and Cohort 2/Group 4 + Cohort 3/Group 2 combined:

In participants without evidence of SARS-CoV-2 infection and in participants with and without evidence of SARS-CoV-2 infection:

- Estimands:
 - GMTs of SARS-CoV-2 Omicron strain (BA.4/BA.5) and reference-strain—neutralizing titers at baseline and 1 month after the study vaccination for each group (Cohort 2/Group 2 + Cohort 3/Group 1 combined and Cohort 2/Group 4 + Cohort 3/Group 2 combined)

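### Does an optional all-available analysis with an undefined 10% trigger leave the Cohort 2 + 3 confirmatory tests exposed to selective exclusion?

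*SAP*

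**What the plan says.** SAP Section 4 bases every immunogenicity endpoint on the evaluable population. To be in it, a participant must be eligible, have received the assigned vaccine, have a valid result from a sample drawn 28 to 42 days after vaccination, and have no other important protocol deviation. An important deviation is one that "in the opinion of the sponsor's clinician, would materially affect assessment of immunogenicity". Membership is settled before unblinding and database release, and "classifications will be documented per standard operating procedures".

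The all-available set needs only receipt of the vaccine and a valid result at some point after vaccination. On its use, SAP Section 4 says "An additional analysis may be performed based on the all-available immunogenicity population if there is a ≥10% difference in sample size" between the two sets. Protocol 9.3.1 has the same optional wording, with the condition "if there is a large enough difference in sample size between" the two populations. SAP 6.1.2.2.1 and 6.2.1.1 list the all-available set where applicable and refer back to Section 4.

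The committed supporting analyses change the method. For the primary tests, SAP 6.1.2.2.2 states: "The unadjusted GMR and 95% CIs will also be calculated based on the Student t distribution". It also adds an unadjusted seroresponse difference. For the reference-strain test, SAP 6.2.1.1 states: "As supportive analysis, the unadjusted GMTs and 95% CIs before study vaccination and 1 month after vaccination will be provided", followed by an unadjusted GMR.

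SAP 2.2 and Protocol 9.1.1 define the target of estimation as the vaccine effect in "the hypothetical setting where participants follow the study schedules and protocol requirements as directed".

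**The concern.** Three features look weak together.

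- The wording is permissive, so nothing obliges the sponsor to run the all-available analysis even when the trigger is met.
- The trigger has no stated denominator or level, and it does not say whether the C4591031 Substudy E comparator counts.
- Sample size is a poor signal. Many exclusions unrelated to titer change nothing, while a few that differ in titer can move the estimate.

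The setting adds to this. The >55-year tests use an external, non-randomised comparator, and the other contrast is between age groups given the same vaccine. Group identity is evident in both, so classification before unblinding protects less than it would in a blinded randomised comparison. The exclusion table in SAP 6.5.2.1 gives counts and reasons, not the effect on a test. At stake would be whether a reader can tell if a confirmatory conclusion depends on who was left out.

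**Working it through.** **Inputs.** From Protocol 9.5: 300 per group, 20% nonevaluable, log-scale SD 1.45 (Omicron) and 1.05 (reference strain), design GMRs of 1.5 and 1, seroresponse 65% v 52% and 65% v 65%. From Protocol 9.1 and SAP 5.1.1: criteria of GMR lower limit >1 or >0.67 (reference strain also needs a point estimate ≥0.8), and seroresponse margins of −5% and −10%. The characteristics of excluded participants are assumptions, because the documents give none.

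**1. The plan's own figures.** 300 × 0.80 = 240 per group. SE of log GMR = 1.45 × √(2/240) = 0.1324, and ln 1.5 / 0.1324 = 3.06. Power is 86.5% by the normal approximation and 86.4% by noncentral t with 478 df (stated 86.4%). The other figures also reproduce: 98.8% (stated 98.8%), 98.1% (98.0%) and 63.2% (63.4%). The 95% CI half-width for the Omicron GMR is a factor of exp(1.96 × 0.1324) = 1.30.

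**2. What the missing definition does.** Excluded participants with a valid result needed to reach 10%, at 240 evaluable per group:

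| Denominator | Per group | Pooled (480) |
|---|---|---|
| Evaluable | 24 (24/240 = 10.0%) | 48 |
| All-available | 27 (27/267 = 10.1%) | 54 |
| Assigned | 30 (30/300 = 10.0%) | 60 |

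The denominator matters little. The level matters more. With 280 v 240 in one group (40/280 = 14.3% to 40/240 = 16.7%) and 245 v 240 in the other (about 2%), the pooled difference is 45/525 = 8.6% to 45/480 = 9.4%, which misses the trigger.

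**3. What exclusions just below the trigger could do to a GMR.** Take 23 excluded in one group and none in the other, so f = 23/263 = 0.0875. If their mean log titer differs from that of the retained by d SDs, restoring them multiplies the unadjusted GMR by exp(f × d × 1.45):

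- d = 0: 1.00
- d = ±0.25: 0.97 to 1.03
- d = ±0.5: 0.94 to 1.07
- d = ±1: 0.88 to 1.13

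One SD is a 4.3-fold titer difference (exp 1.45). It shifts log GMR by 0.0875 × 1.45 = 0.127, or 49% of the half-width of 0.259. If both groups lose the same share with the same d, the shift cancels. With 60 excluded and d = 0 the factor is 1.00.

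**4. Against the criteria, at design values, with the 23 restored to the test group.** The SE uses 263 and 240 participants. For the Omicron GMR it is 1.45 × √(1/263 + 1/240) = 0.129. Seroresponse limits use the unstratified normal approximation.

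| Test | Assumption for the 23 | Estimate | Lower limit | Criterion |
|---|---|---|---|---|
| >55 Omicron GMR | 1 SD lower | 1.5 → 1.32 | 1.02 | >1 |
| 18-55 v >55 Omicron GMR | 1 SD lower | 1 → 0.88 | 0.68 | >0.67 |
| Reference-strain GMR | 1 SD lower | 1 → 0.91 | 0.76 | >0.67, estimate ≥0.8 |
| >55 seroresponse | none respond | 65% → 59.3% | −1.4% | >−5% |
| 18-55 v >55 seroresponse | 40% respond | 65% → 62.8% | −10.6% | >−10% |

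The last test starts at −1.96 × √(2 × 0.65 × 0.35/240) = −8.5%, and reaches about −10.05% if the 23 respond at 46%. It is the only one of the five that crosses under these assumptions.

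**5. What the reader is given without a rerun.**

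- SAP 6.5.1.1: demographics and baseline SARS-CoV-2 status for the safety and the evaluable populations.
- SAP 6.5.2.1: exclusions by group and reason.
- SAP 6.5.2.2: samples inside and outside the time frames.
- SAP 6.5.3.1: a listing of assigned against received vaccine.
- SAP 6.5.3.2: prohibited medications and concomitant vaccines, which are the SAP's own examples of important deviations.

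Serology staff are blinded (SAP Section 5) and samples are coded (Protocol 8.2.4).

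**The case for a change.** The strongest case for a change is that the rerun is cheap. It takes five comparisons with existing programs and leaves alpha, power and success criteria unchanged. It is also the only analysis that would show the effect of exclusions, where the tables show only their number and kind. The 18-55 seroresponse calculation shows that exclusions below the trigger could put the two populations on opposite sides of a margin without the plan requiring anyone to look.

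The textual part stands. The analysis is optional, the trigger is incomplete, and no other committed analysis restores excluded participants. The tables do not re-estimate anything, and these sections do not name the Substudy E comparator.

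The case for a required change does not stand. The all-available set addresses a different question from the stated estimand. It has no sampling window, so it brings back out-of-window samples and other objective exclusions, and a difference between the two runs would not isolate clinician judgement, which is the actual worry. The seroresponse crossing needs one-sided exclusion with a markedly lower response, in a test that already has little margin at its design values. The amendment history in Protocol 10.8 (Amendment 4) also indicates that the 1-month analysis was already done for an interim report, so a commitment made now would be post hoc for these five tests.

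**Conclusion.** No change is needed. Followed as written, the plan gives sound confirmatory results on the population that matches its estimand, and an all-available rerun would alter no success claim. What remains is a missing definition in an optional rule. An analyst who uses the rule can sensibly judge the 10% within each comparison group, name the denominator (24 to 30 participants per group at 240 evaluable), and say whether out-of-window samples count as 1-month results. Showing the all-available result as supportive, labelled post hoc for the 1-month data, is a fair choice for the study report.

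The size of the issue rests on assumptions: 23 exclusions confined to one group, a titer difference of up to 1 SD, point estimates at the protocol's design values, and unadjusted or unstratified approximations. The planned baseline adjustment would change the factors. An observed result close to a criterion could be moved across it by a smaller difference, but that is true of any alternative analysis set. The verdict would change if there were evidence that exclusions depended on titer or differed sharply between groups. The documents contain none.
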